Treatment protocols for patients receiving allogeneic hematopoietic stem cell transplants (HSCT) are more intense and life threatening than other forms of cancer treatment¹⁻⁴. Following transplantation, HSCT patients are at increased risk for a variety of physical side effects, including infections and graft versus host disease (GvHD).^{2,4} *Patient quality of life (QOL) is substantially reduced* following transplantation.⁵⁻¹⁰ Allogeneic HSCT patients require a caregiver 24/7 for the first 100 days and occasionally longer following transplantation to ensure adequate support for the patient.^{11,12} A primary role of the caregiver is to monitor the patient closely for infection, fevers, and features of GvHD as well as to track complex medication regimens, deliver specialized food preparation, and provide transportation to appointments or emergency room visits.^{4,12} Patients and their caregivers are required to move to within 30 min. of the transplant center during the transplant recovery process. Our recent experience working with this group of patients indicated that over 23% of the transplant recipients lived out of state and 46% of all allogeneic HSCT transplant patients had to relocate to temporary housing near the clinic.¹³ In addition to decreased patient QOL, the caregiver is at significant risk for a number of psychosocial problems.¹⁴⁻¹⁸ *Caregiver distress, in turn, is likely to impact the quality of care that a caregiver provides for their patient.* In spite of these issues, there is a gap in interventions focused on coping with stress by the caregivers,¹⁹⁻²² especially allogeneic HSCT caregivers.^{13,14,23,24} Studies of caregiver interventions to mitigate distress have been plagued by small samples, lack of randomization, short follow up periods, problems with blinding, assessment limitations, failure to measure health services utilization by caregivers, absence of biomarkers of caregiver well-being, and caregiver study attrition²⁵⁻²⁷ and *NONE* have focused on the impact on the patient's QOL. Therefore, a significant gap in the evidence base exists with regard to effective caregiver interventions and *their impact on the patients' QOL and medical outcomes.* The present application is pertinent to Criterion 1 as allogeneic HSCT patients have a high burden of chronic medical issues following transplantation with reliance on a caregiver for tangible, informational and emotional support.

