With this background, our group recently completed a randomized control trial (RCT) of an intervention for allogeneic HSCT caregivers with promising results. Our eight session, one-on-one intervention, **PsychoEducation, Paced Respiration, and Relaxation (PEPRR)**,²³ addressed all aspects of the Surgeon General’s Rx. We found at the end of the 100 post-transplant period that caregiver perceived stress (a measure of sense of control and the primary outcome), depression, anxiety, and a summary distress score were significantly reduced in caregivers receiving **PEPRR** compared to Treatment as Usual (TAU) with effect sizes ranging from .39 - .66. However *patient* assessments were limited to medical chart reviews and the Short Form 36 health

questionnaire (SF36)⁴² obtained 1, 3, 6 and 12 months post-transplant. Based on a completers analysis at 6 months post-transplant, there were no differences ($p=.36$) between TAU ($n=35$) and **PEPRR** ($n=35$) on the *SF36 physical* scale which fell below population norms in both groups. However in this small sample we noted a trend for the *patient SF36 mental score* to be slightly higher (e.g., better score, $p=.11$) in the **PEPRR** group compared to TAU as shown in Figure 1. One half of a standard deviation (1 SD = 10 points on the SF36) between the two groups is considered a meaningful clinical difference.⁴³ In spite of continued diminished physical function, the patients whose caregivers received **PEPRR** reported mental health scores in the normal range for healthy people, while those in TAU were lower. Thus our initial success with **PEPRR** for caregivers has pointed to two important paths: 1) the need for verification of changes in patient QOL and 2) extending accessibility and reach of the intervention to include caregivers who might not have been eligible for participation because they lived out of the geographic region of the transplant program.

A.2. Innovation and Potential for Improvement Based on Our Research (Criterion 2)

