Allogeneic hematopoietic stem cell transplant (HSCT) caregivers must be available 24/7 for the first 100 days and often longer following a transplant. However behaviorally and more importantly medically healthy caregivers are essential for the best patient outcome. Few interventions for caregivers have been tested by randomized clinical trials (RCT). Our objective is to determine if a stress management intervention for allogeneic HSCT caregivers compared to self-care relying on resources of the transplant program (treatment as usual, TAU) would be associated with lower stress. We designed a randomized control trial with intent-to-treat of an eight session manualized stress management intervention provided to caregivers following transplant. Subjective behavioral data collected longitudinally for 12 months using standardized instruments was entered blindly. The HSCT caregivers were recruited from a community transplant program between November 2008 and April 2012. The study included a consecutively approached sample of 267 caregivers of allogeneic HSCT patients. 148 (mean age=53.5 years, 75.7% female) were randomized to a manualized intervention (n=74) or TAU (n=74). 101 caregivers reached the three month follow-up with drop outs associated with patient and/or caregiver factors. The intervention included an eight session stress management program provided to caregivers by a social worker during the immediate post-transplant period that focused on learning about stress, changing role(s) of the caregiver, cognitive behavioral approach to managing stress, paced respiration with a commercial biofeedback device, and identifying resources. A panel of questionnaires and physiological markers was collected from the caregivers five times over the course of one year beginning in the peri-transplant period. The primary outcome measure was self-reported perceived stress. Secondary outcome measures included depression, anxiety, caregiver burden, physical health, sleep, trauma and composite scores of these measures. Groups did not differ at baseline. Controlling for age, the intervention resulted in significantly lower ($p=0.039$) caregiver perceived stress (primary outcome) at 3 months post-transplant (Mean=20.0, SD=1.0) compared to TAU (Mean=23.0, SD=1.0) with an effect size (ES) of 0.39. The intervention group showed significantly better ($p=0.019$) scores on a secondary composite score that includes depression, anxiety, and other distress measures (Mean=-0.22, SD=0.13) compared to TAU (Mean=0.23, SD=0.13) with an ES of 0.45. This study had limitations due to problems with low minority subject recruitment, logistics of collecting dependent measures when patients and caregivers moved out of the area, as well as missing data. While needing further study within more settings, this approach is likely to improve caregiver well-being and potentially that of patients.

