Data Aggregation, Distributional Assumptions, Missing Data/Attrition. Data will be screened for errors and outliers. Appropriate transformations will be made for non-normal outcomes. The pattern of participant dropout will be examined to ensure a reasonably equal distribution of participants lost to follow-up between groups. The analytic approach proposed uses maximum likelihood techniques that can include participants with incomplete data without need for imputation. These techniques are robust under certain conditions such that group comparisons will not be biased as long as missing data is ignorable.^{132,133} If this is not sufficient to minimize influences of particular observations, a sensitivity analysis will be conducted to help determine effects of missing data. Separate analyses of only those participants who complete the study will be conducted.

Verification of Randomization and Inclusion of Covariates. Preliminary analyses will validate that there are no baseline differences between intervention groups. We expect baseline differences will be accounted for by randomization, but should differences remain we will co-vary variables that are both correlated with the outcome and that differ by group.

Analytic Strategy In general, outcomes will be analyzed with linear mixed models comparing intervention (**fPER**, TAU) in patients and caregivers separately. An alpha level of 0.05 will be used to evaluate significance of the a priori planned comparisons. Two-tailed tests are proposed in order to detect differences between **fPER** and TAU in either direction. The software SAS PROC MIXED will be used.¹³⁴ The analytic aims and hypotheses are briefly stated, followed by overall analytic plan for primary and secondary outcomes:

Aim 2: Assess patient QOL following an allogeneic HSCT by the FACT-BMT as the primary patient outcome. Patients whose caregivers receive fPER will have improvements in FACT-BMT compared to TAU.

Aim 3: Test impact of fPER on caregiver composite distress score of depression, anxiety, and stress as the primary caregiver outcome. Caregivers who receive fPER will have reduced distress compared to TAU.

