For hypotheses addressing group differences for patients and separately for caregivers, outcomes will be evaluated with the same design: 2 groups (**fPER**, TAU) at 2 clinics (CBCI, UCH) over 4 times (prior to transplant, 6 wks., 3 mo., 6 mo.). Mixed models will specify group, clinic, time, and their interactions as fixed effects and subject as a random effect, where subject is assumed independently normally distributed with mean 0 and variance independent of the random errors. The primary caregiver model of composite distress will include caregiver age as a covariate because it related to caregiver distress in our prior study¹¹; secondarily, we will investigate inclusion of patient FACT-BMT as a covariate. The primary patient model of FACT-BMT will include no covariates, but secondarily will explore inclusion of caregiver distress as a covariate.

Aim 4: Assess biomarkers of allostatic load in patients prior to transplant and caregivers during the transplant process using novel biomarkers. Patient's hair cortisol will predict their QOL and distress at the beginning of the transplant process. fPER will be associated with reduced allostatic load in caregivers who receive fPER compared to those receiving TAU.

Linear mixed models will similarly be used to evaluate group differences in these biomarkers separately in patients and caregivers. Caregiver age and patient FACT-BMT will be evaluated for inclusion in caregiver models. Caregiver composite distress score will be evaluated for inclusion as a covariate in patient models.

Subject sample size and power analysis. Our prior trial demonstrated medium effect sizes (0.39-0.45) for PEPRR in caregivers. We believe the proposed modifications in **fPER** will likely increase its effect for caregivers. However, the effect of **fPER** on

Table 2. Minimum detectable effect sizes with specified sample size and power

Sample Size Per Group	80% Power	85% Power	90% Power	95% Power
112 Dyads	0.19	0.20	0.22	0.24
74 Dyads	0.23	0.25	0.27	0.30
62 Dyads	0.25	0.27	0.29	0.32

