patient QOL is indirect, and thus smaller effect sizes would be expected. We estimated minimum effect sizes detectable for different power specifications for a recruited sample size of 112 per treatment group and also for smaller sample sizes, allowing for increased variability due to estimated losses to follow-up of 34% at 3 mo., and 45% at 6 mo. based on our prior caregiver trial. Estimates are conservative since **fPER** has been specifically modified to reduce attrition. 112 dyads (consisting of a caregiver and patient) randomized to each group provide excellent power (>95%) for detecting the medium effect size expected for the composite distress score in caregivers and are necessary to provide adequate power (80-85%) for detecting smaller effect sizes expected for the FACT-BMT QOL measure in patients. Estimates are also conservative because mixed model analyses that include all subjects (even those with only a single observation) have been shown to provide the greatest power.¹²⁷

G. Summarize Knowledge to be Gained:

This study will provide empirical evidence regarding both behavioral and possible physiological efficacy of a stress management psychoeducation program for caregivers and the impact on patient QOL. This is one of the few studies of its kind that promises to provide not only information regarding behavioral outcome for the patients as far as quality of life but also impact their caregivers. The results of this study will lead to the availability of a manual developed for this intervention that can be disseminated to other HSCT programs leading to improved patient QOL and reduced caregiver distress.

H. References:

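### Distance from the clinic is a main motive for fPER and a known data-collection problem, but no model, comparison or dropout check uses it, so a possible bias at later visits could go unseen

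*Combined protocol and SAP*

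**What the plan says.** Distance is prominent in the rationale. Section II, A.1 reports that "46% of all allogeneic HSCT transplant patients had to relocate to temporary housing near the clinic". It names two paths from the prior trial: verifying change in patient QOL, and "extending accessibility and reach of the intervention to include caregivers who might not have been eligible". A.2 calls the same 46% distant caregivers, and the Smartphone paragraph of IV.C says some relocated dyads went home early and missed later sessions. Section III lists among the prior trial's limitations "logistics of collecting dependent measures when patients and caregivers moved out of the area, as well as missing data". The fPER description in IV.C expects the modified programme to improve retention, and the power section of IV.F says it was changed to reduce attrition.

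The analysis in IV.F does not use distance. The mixed models contain group, clinic, time and their interactions, with a random subject effect. Caregiver age is added for caregivers; for patients, "The primary patient model of FACT-BMT will include no covariates". Dropout is to be compared between arms only. Another baseline variable enters only if it both correlates with the outcome and differs by arm. The justification for the likelihood approach is that "group comparisons will not be biased as long as missing data is ignorable". The demographic items listed in IV.D include no residence item. Section IV.E separately states that the last valid measure is carried forward and that dropout is treated as completely at random unless otherwise indicated.

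**The concern.** A likelihood analysis ignores missingness safely only when whatever drives the loss is in the model or is captured by earlier outcomes that are. Distance is a driver that the protocol itself points to. If it also relates to outcome or to the size of the effect, a model without it need not meet the stated condition.

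There are two routes to bias. First, video delivery may keep distant fPER dyads in follow-up while distant TAU dyads leave. The arms then differ in their mix of distant and local dyads at later visits, although they were balanced at randomisation. If distant patients do better or worse than local ones, the contrast shifts even with a constant effect. Second, if distant dyads are lost more often in both arms and fPER works differently for them, the late contrast averages over a different mix from the one randomised. The covariate rule cannot catch either route, because a variable balanced at baseline never qualifies.

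The plan would also yield no estimate of how fPER performs for the families that video chat was meant to reach.

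**Working it through.** **Inputs from the documents.** A "recruited sample size of 112 per treatment group"; losses of 34% at 3 months and 45% at 6 months, overall only; two-sided alpha 0.05; 46% distant in the prior trial.

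**Assumptions.** The 46% carries over. All splits of loss, effect and outcome by distance are assumed, since none is given. Within-person correlation is 0.5. I look at 6 months because loss is largest there; IV.F names no single primary visit.

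**Step 1: the plan's own figures.** 112 × 0.66 = 73.9 and 112 × 0.55 = 61.6, which give the 74 and 62 dyads in the power table. Its entries reproduce only as half the usual standardised difference: (1.960 + 0.842) × √(2/112) = 0.374, and half of that is 0.187, printed as 0.19. Sizes below are on the full scale, in SD units. The table's scale is a separate matter.

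**Step 2: shift among dyads observed at 6 months.** The distant share among those retained is 0.46·rD / (0.46·rD + 0.54·rL), where rD and rL are distant and local retention.

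- A, mild, same in both arms: rL = 0.60, rD = 0.49. Share = 0.2254/0.5494 = 0.410. With effects of 0.1 SD local and 0.4 SD distant, the shift is (0.46 − 0.410) × 0.3 = 0.015.
- B, strong, same in both arms: rL = 0.70, rD = 0.37. Share = 0.1702/0.5482 = 0.310. Same effects: (0.46 − 0.310) × 0.3 = 0.045.
- C, retention differs by arm: rL = 0.55 in both; rD = 0.70 under fPER and 0.40 under TAU. Shares are 0.322/0.619 = 0.520 and 0.184/0.481 = 0.383. With a constant effect and distant patients 0.3 to 0.5 SD worse by 6 months, the shift is 0.138 × 0.3 = 0.041 to 0.138 × 0.5 = 0.069.
- If distant and local retention are equal, every share is 0.46 and the shift is zero.

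**Step 3: shift in the planned likelihood model.** A random-intercept model on four visits uses the earlier data and recovers part of this.

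| Scenario | Observed dyads only | Planned model |
|---|---|---|
| A | 0.015 | about 0.013 |
| B | 0.045 | about 0.037 |
| C | 0.041–0.069 | 0.034–0.057 |

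Hence about 0.01 to 0.06 SD. In B the true average is 0.46 × 0.4 + 0.54 × 0.1 = 0.238. The direction depends on the assumptions: a larger local effect, or better outcomes in distant patients, reverses it.

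**Step 4: what each extra term buys, at 112 per arm.**

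- In C, adding relocation and relocation-by-time removes the bias and raises the SE by about 0.001.
- In B those two terms do not help, because the mix is the same in both arms. Relocation-by-group-by-time, averaged over the randomised mix, removes the bias of 0.037 but raises the SE from 0.166 to 0.173. Root mean squared error is √(0.037² + 0.166²) = 0.170 for the planned model and 0.173 for the larger one, so accuracy does not improve.

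**Step 5: precision by distance, equal 45% loss.** Distant: 112 × 0.46 × 0.55 = 28.3 per arm. Local: 112 × 0.54 × 0.55 = 33.3. The difference detectable with 80% power is 2.802 × √(2/28.3) = 0.74 SD for distant and 0.69 for local dyads. The SE of the interaction is √(2/28.3 + 2/33.3) = 0.36. The detectable interaction is therefore 1.01 SD, the 95% CI half-width about 0.71, and the power for an interaction of 0.4 SD about 20%.

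**The case against.** A reader might infer that the 6-month effect is weighted toward local dyads. The documents do not show this. They give loss only overall, and Section III attributes dropout to patient or caregiver factors. IV.C links going home early to missed sessions rather than missed assessments. Section II, A.1 also has dyads living within 30 minutes of the centre during recovery, so distance would act mainly on late visits. Much of the loss may be death, which IV.E names and which need not depend on distance. All of this stands and is why the bias is stated as conditional. Section III does, however, tie moving away to trouble collecting measures.

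A reader might also infer that distance is the reason fPER exists. It is one of several: verifying patient QOL comes first, and the device change, the pre-transplant start and the booster sessions are others. Reach is in no aim or hypothesis, so no stated hypothesis goes untested.

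The strongest statistical objection is that putting the three-way term in the primary models buys nothing in accuracy, even in the strong scenario. Step 4 bears this out, so that term belongs in a secondary analysis. Under last value carried forward, distant dropouts would stay in the 6-month comparison and the weighting would not arise in this form. That also stands, and it makes reconciling IV.E with IV.F the first task.

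**Conclusion.** The omission is real and cheap to repair; the bias is possible, not demonstrated. It requires loss that depends on distance, together with either arm-specific retention of distant dyads and an outcome that varies with distance, or an effect that differs by distance. The first combination is plausible because fPER is meant to improve retention. Under the assumed splits the shift is about 0.01 to 0.06 SD, at most about a third of the SE of the contrast (0.057/0.166 = 0.34). It is not negligible where the protocol itself expects smaller effects on FACT-BMT. The sizes rest on the assumed retention, effects, drift and correlation of 0.5, and on the likelihood model of IV.F being the one used. The documents do not support saying that the trial's result will be biased, or in which direction.

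**What to change.** 1. Reconcile IV.E (last value carried forward, dropout completely at random) with IV.F (likelihood without imputation), so that one missing-data approach governs the primary analysis.
2. Record pre-transplant residence at baseline as within clinic reach, yes or no, for instance by the protocol's own 30-minute threshold. IV.C mentions contact information on the code sheet, but no residence variable is listed, so it should be defined rather than presumed available.
3. Add relocation and relocation-by-time to the patient and caregiver mixed models in IV.F.
4. Extend the dropout check to retention by arm and distance.
5. Pre-specify, as a sensitivity or secondary analysis, the model with relocation-by-group-by-time, averaged over the randomised mix. Report local and distant fPER–TAU differences with 95% CIs as estimates, not powered tests.

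The cost is one baseline item, SAP wording and a few degrees of freedom. The distance-specific estimates will be imprecise, with about 28 distant dyads per arm at 6 months.

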450 total adult subjects (225 patients and their 225 caregivers) will be randomized as pairs by permuted block into treatment as usual (TAU) or “fone” PsychoEducation and Relaxation (**fPER**). A total of 112 caregivers (distributed proportionally in relation to patient pool across the two sites and ethnic and racial category) will be randomly assigned to TAU and 113 to **fPER** after completing baseline assessments as shown in Table 1. The expected age range of caregivers and patients is expected to 18-85 years of age. It is unlikely that anyone under the age of 21 will be a caregiver for an allogeneic HSCT patient and HSCTs are not performed for children by either program. Should a younger caregiver present themselves, we will reevaluate the lower cut off. Although caregivers are expected to be generally healthy, we will exclude individuals who are taking steroidal medications for allergy or inflammatory disorders. These medications are most likely to confound the hair cortisol assessments. Medication use by caregivers will be treated as a covariate in secondary analyses. Eliminating caregivers who use any medication(s) would skew the nature of the caregiver sample so that the subjects in the intervention would be only the very healthy. Such selection would distort the potential impact of the intervention on biomarkers and behavior for the population overall.

[figure not shown]
Group Condition	Site 1 - UCH	Site 2 – CBCI
TAU + Manual	37	75
fPER	38	75
Total (225 dyads)	75	150

Patients: Inclusion criteria include: 1) receiving an allogeneic HSCT, 2) able to read and speak the English language, and 3) telephone access.

Caregivers: Inclusion criteria include: 1) the person in the patient’s life who is primarily responsible for care decisions, emotionally invested in the patient’s care, provides instrumental care such as transportation, and available if randomized to the fPER group to participate in the majority of intervention sessions, 2) be able to read and speak the English language, 3) willingness to use a Smartphone, 4) absence of a serious medical condition likely to influence cortisol assessment in their hair, 5) alcohol consumption less than 2 drinks/day, 6) no steroid medications, and 7) at least 18 years of age.

Patient and caregiver *exclusion criteria* include a history of a psychiatric illness *unrelated to the HSCT* within the past 18 months. Children under the age of 18 do not receive HSCTs in either program.

[figure not shown]

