Collaborating Sites: The two study sites include Presbyterian St. Luke’s Medical Center/Colorado Blood Cancer Institute (CBCI) – Site 1 and the University of Colorado Hospital (UCH) – Site 2. There are currently no other caregiver interventions studies offered at either site that would compete or limit subject availability for the present study. Projected enrollment from each site over 27 mo. is given in the adjacent figure.

C. Study Design and Research Methods:

Subject flow for **fPER** and TAU is indicated in Figure 4. Following consent (both members of the dyad must consent), patients and caregivers will complete a panel of questionnaires and provide a baseline hair sample. Only caregivers will provide blood samples for DNA, lymphocyte and plasma banking. After completing baseline measures, subjects will be assigned to treatment group by permuted block design known only to site coordinators ([name] and [name]) and interventionists. The first intervention session for **fPER** assignment will begin as soon as possible after consenting *prior to transplant*. Collection time is anchored to the day of transplant as day 0 for statistical analysis. The subsequent questionnaire collections for both patients and caregivers will be at approximately +6 weeks and +3 and +6 months post-transplant. Hair and blood samples will only be collected post-transplant from caregivers at 3 and 6 months. Hair will be collected from the patients pre-transplant and at +6 months post-transplant. *For those patients who have previously been on either steroid medications or chemo prior to conditioning, this information will be recorded for this exploratory study of hair cortisol in the patients.* These samples are collected for exploratory analysis only. Caregivers will provide hair samples on three occasions at baseline prior to randomization and three and six months after their patient’s transplant. Hair is removed from the posterior vertex of the scalp at a proximal level using thinning shears. This region is more resistant to hair loss in male pattern baldness (e.g., one of the last areas to be lost). Cosmetically one cannot tell the hair was removed. For subjects without adequate hair this will be treated as missing data. However the [name] laboratory has developed an approach that permits the assay of far less hair (1/10 of most published reports) which allows for receding hair lines and shorter hair in males.

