Figure 4. Study timeline common to CBOI (n=150) and UCH(n=75) sites with randomization by permuted block design for caregivers. Patients (indicated by +P) will provide a hair sample *only* at baseline and no blood samples beyond routine clinical assessments but they will complete questionnaire in tandem with caregivers. **Key to Sampling**

At each phase, patients and caregivers will complete the same battery of questionnaires that includes the Center for Epidemiological Studies-Depression scale (CES-D), the perceived stress scale (PSS), Pittsburgh Sleep Quality Inventory (PSQI), and the State-Trait Anxiety Inventory (STAI). Additionally the patient will complete the FACT-BMT each time while the caregiver completes the Caregiver Reaction Assessment (CRA). Both the patient and the caregiver will additionally complete a demographic questionnaire that includes questions regard age, diagnosis, income, and other standard questions regarding nutrition, health behaviors, and health services utilization. At study completion, an exit questionnaire will address each subject’s evaluation of the study and the group in which they were assigned. Each subject will be assigned a code number for de-identifying purposes at consenting and this number will be the only identifier on questionnaires. The confidential code sheet that identifies the subject’s randomized treatment group based on a permuted block design, subject name, and contact information will be kept in a locked cabinet as well as in a password protected secure data base. After the randomization table is created by the biostatistician, this will be available only to Drs. [name] and [name].

Intervention groups
TAU. All patients and caregivers, regardless of randomization, are informed of what to expect during the transplant process and how to locate available support resources within each program. Patients and caregivers

are given information that is specific to their involvement in the transplantation process and recovery phase. Subjects randomized to TAU will be encouraged to participate in available support programs at their respective centers which are very similar between sites and include individual counseling as well as support groups. Due to the impact of our prior intervention on caregiver distress, we will provide each caregiver randomized to TAU a workbook prepared for someone to use without one-on-one sessions with a therapist.

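### Site coordinators and interventionists may know the permuted-block design, and no concealed release is described, so later assignments could be foreseen

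*Combined protocol and SAP*

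**What the plan says.** Section IV.B states that patients and caregivers "will be randomized as pairs by permuted block into treatment as usual" or fPER, with 112 and 113 dyads planned. It gives no block size and does not say whether block size is fixed or varied.

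Section IV.C makes two statements about who knows what:

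- Early in the section, subjects are "assigned to treatment group by permuted block design known only to site coordinators" (two names follow, removed from the public text) and interventionists.
- Later, before the description of the intervention groups: "After the randomization table is created by the biostatistician, this will be available only to Drs", followed by two names that were removed from the public text.

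Three safeguards appear in IV.C. Assignment comes late, after both members of the dyad have consented: "After completing baseline measures, subjects will be assigned to treatment group by permuted block design". The biostatistician creates the table. The code sheet linking each subject to a group "will be kept in a locked cabinet as well as in a password protected secure data base".

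The plan describes no central or web release, no sealed envelopes, and no rule that keeps the sequence or block structure from those who screen, approach or consent dyads.

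**The concern.** Blocking forces the arms to balance within each block, so earlier assignments carry information about later ones. That is harmless only if recruiting staff cannot combine the block structure with the assignments already made.

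Past assignments cannot be hidden here. fPER caregivers receive ten sessions and an emWave2; TAU caregivers receive a workbook without sessions. No blinding of participants, interventionists or coordinators is described. Read literally, the first statement in IV.C supplies the missing element by letting coordinators and interventionists know the block design. The second puts the whole table in the hands of two people whose part in recruitment is not stated.

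Someone who foresees the next arm can influence which dyad is approached and when, how hard consent is encouraged, or how a borderline criterion is judged. One caregiver criterion in IV.B needs exactly such judgement: whether the caregiver would be able to attend most sessions if allocated to fPER. The groups could then differ before treatment starts, in ways that measured covariates need not capture.

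**Working it through.** **Inputs.** Allocation is close to 1:1. The IV.B table gives TAU 37 + 75 = 112 and fPER 38 + 75 = 113, together 225. Block size is not in the documents, so sizes from 2 to 10 are assumed. The plan states no figure for predictability, so there is none to reproduce.

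**Setting.** An observer knows the fixed block size and all past assignments in the stratum. Write the block size as b = 2h, with h places per arm.

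**Share known with certainty.** An assignment is forced once one arm is used up, that is, within the final run of the block. The expected length of that run is 2h/(h + 1), so the share is [2h/(h + 1)]/(2h) = 1/(h + 1).

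Check by listing for b = 4: there are 6 balanced sequences. Two end in a run of two and four in a run of one, so 2×2 + 4×1 = 8 of 24 assignments are forced, or 33%.

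Check for b = 6: there are 20 sequences. Twelve end in a run of one, six in a run of two and two in a run of three, so 12 + 12 + 6 = 30 of 120 are forced, or 25%.

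**Best-guess accuracy.** With a and c places left in the two arms, the best guess is right with probability max(a, c)/(a + c). This is averaged over positions.

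- b = 4: (1/2 + 2/3 + 2/3 + 1)/4 = 0.708.
- b = 6: (0.5 + 0.6 + 0.6 + 0.7 + 0.7 + 1)/6 = 0.683.

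| Assumed block size | Certain in advance | Of 225 dyads, about | Guessed correctly |
|---|---|---|---|
| 2 | 50% | 113 | 75% |
| 4 | 33% | 75 | 71% |
| 6 | 25% | 56 | 68% |
| 8 | 20% | 45 | 67% |
| 10 | 17% | 38 | 65% |

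Without foreknowledge a guess is right 50% of the time. With the table, 100% is known. The dyad counts ignore incomplete last blocks.

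**Applying this to the two statements in IV.C.**

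- *Literal reading.* Coordinators and interventionists know the block design and, through their work, past assignments. The block rows of the table apply to them.
- *Milder reading.* They know only assignments already made. They would still have to learn or infer the block size, which a small fixed block makes easier.
- *Either reading.* The two doctors have the table, so the 100% figure applies to them.

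**The case against.** **The two statements need not conflict.** One concerns the block design, the other the table. Two people can hold the table while coordinators and interventionists are told each arm so that they can act on it. With names removed, the two doctors may be the two coordinators. A reader might infer a contradiction, but the documents do not prove one. What stands is that both statements use the word only, interventionists appear in just one of them, and neither describes how an assignment is released. If the doctors are the coordinators, site staff hold the full list.

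**Advance disclosure to recruiters is not stated.** A reader might infer that those who enrol dyads hold the sequence. The documents do not say who enrols, nor that the table holders do.

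**Assignment follows dual consent and baseline.** This protects the baseline answers. It also weakens the link between foreknowledge and recruitment: the percentages concern the next assignment, whereas approach and consent come earlier. At 225 dyads over 27 months, about 8 a month (225/27 = 8.3), several dyads may be in process at once. The protection is real but partial.

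**The prior trial is no evidence of selective approach.** A reader might take the fall from 267 caregivers approached to 148 randomised (Section III) as room for it. That sample was approached consecutively, so the fall reflects losses after approach.

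**Concealment does not cure everything.** It guards against selection bias. It does nothing about expectation effects in self-reported outcomes when the arms are known.

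**Conclusion.** The concern holds as a weakness in allocation concealment. Followed literally, IV.C lets coordinators and interventionists know the block design in a trial where past assignments are visible, gives two doctors the table, and describes no concealed release. With assumed fixed blocks of 4 or 6, a third or a quarter of assignments would be certain in advance, and 71% or 68% could be guessed. With the table, all would be known. These figures depend on a block size the plan does not give and on the observer knowing both it and past assignments.

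This is a risk, not demonstrated bias. A reader might want to turn predictability into a bias in the treatment effect or an inflated type I error. The documents do not support that. It would need an assumed shift in outcome from selective enrolment, the true block size and the numbers retained after the planned-for losses. It would also need an allowance for the pre-transplant measurement that is one of the four times in the mixed model, and for the planned adjustment for baseline differences.

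**What to change.** Replace both sentences in Section IV.C with one rule:

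- The biostatistician who creates the sequence holds it. Block sizes vary at random, are not disclosed, and apply within the strata the plan already intends.
- Each assignment is released singly, for example by sealed opaque envelope or by the biostatistician on request, and only after both members of the dyad have consented and completed baseline.
- Nobody who screens, approaches or consents dyads sees the table or the block sizes.
- Coordinators and interventionists learn only the arm of dyads already assigned.

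The cost is protocol wording and a small administrative step for each of the 225 dyads. Someone must be available to release assignments promptly, because the first fPER session is meant to take place before transplant. Sample size, power and alpha do not change.
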